## Pathways to developing MSDs

The primary pathways to occurrence of MSDs are

- ➤ Central nervous system (CNS) recognition of the forceful and repetitive task leading to altered sensation and motor abilities which result in WRMSDs
- ➤ Forceful and repetitive task causes tissue injury leading to acute or chronic inflammation depending on the duration. This then leads to tissue fibrosis which finally causes WRMSDs.
- ➤ In the third pathway, forceful and repetitive task leads to either pathological remodeling which results in reduced biomechanical tolerance and finally causing

WRMSDs, or adaptive remodeling to compensate for the exertion. (Barbe & Barr, 2006). However, it is worth noting that these pathways do not work in isolation but are interconnected and interrelated. (Grote, 2019)

## **Association between Age and MSDs**

Several studies have established association between age and development of MSDs. (Heiden, Weigl, Angerer, et al.2013) revealed that the frequency of developing MSDs increased significantly with age among nurses in Germany Darragh, Huddleston and King (2009) also reported that age of 55 years and above is significantly associated with the development of WRMSDs among occupational therapist. Further, (Janwantanakul, Pensri, Jiamjarasrangsri, et al. 2008) reported that younger workers (<30 years) were more prone to experience WRMSDs of the upper limb compared to

those older than 49 years. Again, The mean age (SD) of monks was 60.4 (12.7) with knee osteoarthritis Among monks in Songkhla province in the southern part of Thailand. (Tangtrakulwanich, et al 2006) In a recent study, age was found to be significantly associated with occurrence WRMSDs in the lower back, neck and upper back (Yan et al., 2017). In contrast to all these studies, (Landau, Rademacher, Meschke, et al., 2008) reported no significant association between age and development of MSDs and suggested that this could be due to the assignment of certain job task to certain specific workers.

#### **Association between sex and MSDs**

Only few studies analyzed the association between sex and MSDs (Janwantanakul et al., 2008; Darragh et al., 2009; Mohanty, Singh, & Pattnaik, 2017). reported that females were more predisposed to developing WRMSDs as compared to their male counter parts. Similarly, reported higher prevalence of MSDs in females as compared to their male counter parts. Females were found to have higher prevalence of MSDs compared to male counter parts by (Campo et al., 2008). (Yılmaz, et al., 2008) Tantawy et al. (2017) reported that Age and sex standardized incidence rate of hand

OA is 100/100,000 person-years. Women are affected much more frequently than men, at a ratio of about 10:1. These results can explain by the fact that females general have weaker bodies so they are more predisposed to the development of MSDs.

### Association between Work demand and MSDs

Significant association between work demand and development of MSDs has been 0established by several studies. The higher the work demand on the worker, the more likely he or she becomes predisposed to the development of MSDs. **Heiden et al.** (2013) reported that high levels of physical task correlates to higher risk of developing MSDs.

Merakou, et al (2017) showed that monks living in communal monasteries estimate their physical health to be better than the monks who live in skete and Orthodox Christian way of life constitutes a successful pattern of mental health but not for physical health. Yan et al. (2017) found that excessive workload and poor postures were the risk factors for the development of MSDs.

#### Association between Years of ordination and MSDs

Monks had a high prevalence of MSD overall. Happens to all parts of the body. The factors that were more associated with MSD symptoms were age, ordination years. Whaikit, et al (2020).

Merakou, et al (2017) showed that increased age, living in a skete, increased years in Monasticism, having a physical, mental problem and MSDs. The study of Rodopaios, N. E., et al (2020) investigated the possible effects musculoskeletal metabolism, on bone density in monks over 10 years of ordination.

Samerchua, et al (2017) The number of years of ordination can have a significant positive correlation with BMI. So the sedentary lifestyle for a prolonged period of ordination could increase the risk for MSDs. MR, & Asha, 2020).

So we can Take into consideration the relationship between Years of ordination and MSDs

# **Chapter 3**

# Subjects, Materials and Methods

This study will be conducted at several monasteries in Egypt to make correlation between musculoskeletal disorders and monastic years among monks and nuns.

**Study design:** Observation study - cross-sectional survey.

**Participants:** sample size of monks will be 400 subjects of both genders (monks and nuns) randomly selected from different monasteries, Participants aged from 24 years old and above thought monastic years. As:

- (1-3) years "novice" or "probationary"
- (4-10) years of monasticism
- more than 10 years of monasticism

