## Purpose of the study

This study will be conducted to:

- 1- Survey the relationship between duration of years since ordination and musculoskeletal disorders among Egyptian monks.
- 2- Survey the relationship between musculoskeletal disorders and gender of monks and nuns.

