#### **Inclusion criteria:**

- 1- Both genders will include in study.
- 2- Monks and nuns work in different works administration.
- 3- Age starts from 24 years old and more. (Merakou, et al., 2017)
- 4- Body mass index (BMI) between 18.5 to 24.9 kg/m2 (Van, et al., 2023)

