## **Statistical Analysis:**

Descriptive statistics of mean and standard deviation, frequencies, percentage and confidence interval (CI) are utilized in presenting the subjects demographic and musculoskeletal disorders data. Person's chi – square statistic and logistic regression is utilized to examine associations between musculoskeletal disorders prevalence and years of ordination. The level of significance for all statistical tests is set at p<0.05. All statistical measure will be performed through the statistical package for social studies (SPSS version 22 for windows)

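### Years of monasticism are recorded on the form, but the only coding the plan defines is three bands with an open top, and the analysis section does not say that the regression uses the recorded years

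*SAP*

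**What the plan says.** Purpose 1 is to "Survey the relationship between duration of years since ordination and musculoskeletal disorders among Egyptian monks". Hypothesis 1 is the matching null, that years and musculoskeletal disorders (MSD) are unrelated.

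Delimitations and Chapter 3 (Participants) give the same three bands: 1-3 years (novice or probationary), 4-10 years, and "more than 10 years of monasticism". The age criterion is "Age starts from 24 years old and more", with no ceiling, so nothing caps the top band.

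The questionnaire description lists duration of ordination among the items in section A, and the Appendix II form has an open field for years of monasticism with no bands printed.

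The Statistical Analysis section plans chi-square and logistic regression to "examine associations between musculoskeletal disorders prevalence and years of ordination". It mentions neither the bands nor recorded years as a continuous term. On size and level the plan states "sample size of monks will be 400 subjects of both genders" and "The level of significance for all statistical tests is set at p<0.05".

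**The concern.** Two of the three bands describe the first decade, and all later variation in exposure falls into one cell. A chi-square test needs categories, and these bands are the only ones supplied. For the regression, the analyst could choose either coding after seeing the data.

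Hypothesis 1 is a null, so a weak test works in its favour. If MSD rises gradually with years, a banded test has less chance of detecting it than a test on the years already recorded, and a non-significant result could be reported as no relation with years. An ordered test on the same bands does not cure this, because most of the loss lies inside the top band.

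**Working it through.** **Inputs from the SAP.** N = 400; alpha 0.05 (sidedness not stated, taken as two-sided); bands 1-3, 4-10 and over 10 years. The SAP gives no power, effect size or spread of years, so it has no power figure to reproduce. The spread of years is an assumption throughout and is varied.

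**Step 1: information kept.** For a linear relation, the share of the noncentrality that a three-group chi-square keeps is

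kept = between-band variance of years / total variance of years.

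Worked case, whole years spread evenly over 1-40:
- Band shares are 3/40 = 0.075, 7/40 = 0.175 and 30/40 = 0.75. Band means are 2, 7 and 25.5, and the overall mean is 20.5.
- Total variance = (40² − 1)/12 = 133.25.
- Between bands = 0.075×18.5² + 0.175×13.5² + 0.75×5² = 25.67 + 31.89 + 18.75 = 76.31.
- Kept = 76.31/133.25 = 0.57, so 43% is lost.
- Within the top band = 0.75×(30² − 1)/12 = 56.19, and 56.19/133.25 = 0.42. So 42 of the 43 points are lost inside the top band.

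**Step 2: power.** Set the slope so that recorded years as one linear term have 80% power at N = 400 (noncentrality 7.849, 1 df). The banded chi-square (2 df) then has noncentrality 7.849 × kept, and the N that restores 80% is 400 × 9.635/(7.849 × kept). For uniform 1-40 this is 400 × 9.635/(7.849 × 0.573) ≈ 857.

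| Assumed spread of years | In top band | Lost | Banded power | N for 80% with bands |
|---|---|---|---|---|
| Uniform 1-20 | 50% | 17% | 62% | 591 |
| Uniform 1-30 | 67% | 31% | 54% | 710 |
| Uniform 1-40 | 75% | 43% | 46% | 857 |
| Uniform 1-50 | 80% | 51% | 40% | about 1,010 |
| Exponential, mean 5, cut at 50 | 14% | 20% | 60% | 617 |
| Exponential, mean 10, cut at 50 | 36% | 33% | 53% | 728 |
| Exponential, mean 20, cut at 50 | 57% | 41% | 47% | 833 |
| Equal thirds, top 11-20 | 33% | 12% | 65% | 559 |
| Equal thirds, top 11-40 | 33% | 21% | 60% | 618 |
| Equal thirds, top 11-50 | 33% | 23% | 59% | 637 |

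**Step 3: simulation with a stated effect.** N = 400, prevalence linear on the logit scale from 45% at 1 year to 65% at 40 years (assumed), 3,000 surveys per row:

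| Assumed spread | Chi-square on bands | Trend test on bands | Recorded years, 1 df |
|---|---|---|---|
| Uniform 1-20 | 13% | 18% | 21% |
| Uniform 1-30 | 23% | 28% | 41% |
| Uniform 1-40 | 31% | 38% | 64% |
| Uniform 1-50 | 44% | 49% | 83% |
| 1 + exponential mean 12, cap 50 | 33% | 40% | 65% |
| Equal thirds, top to 40 | 43% | 51% | 63% |

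A separate set of runs gave 36/42/68% for uniform 1-40 and 48/53/67% for equal thirds with the top band to 40. The difference is of the size produced by drawing years as whole numbers instead of fractions. The ordering is the same.

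**Step 4: relation flat to year 10, rising afterwards.** The bands still keep about 45% of the signal (uniform 1-40), 47% (exponential mean 10) or 68% (equal thirds, top 11-40), because the rise lifts the top band's average. A linear term in recorded years keeps 97%, 90% and 94%.

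**The case against.** The strongest reply is that the SAP does not commit to a banded analysis. The bands stand under Delimitations and Participants, which describe who is surveyed, and the planned logistic regression could take years as recorded, in which case nothing is lost. This is right as far as it goes, and it makes the point conditional for the regression. It does not remove the point: the chi-square must use categories, and the regression's exposure term is left open.

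A reader might infer that the bands are blind to everything after year 10. Step 4 shows otherwise: only the shape inside the top band is invisible.

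A reader might also infer that about half of the information is lost. That needs years spread evenly to roughly 40-50. With about equal numbers per band, which is as plausible as the long spreads, the loss is 12% to 23%.

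The power of recorded years in the tables belongs to a single linear term, and the data were generated as linear. A joint 2-df test of linear plus quadratic terms reaches about 56%, 76% and 52% under uniform 1-40, uniform 1-50 and the exponential with mean 12. With equal thirds and a top band ending at 20, 30, 40 or 50 years, it gains only about 1, 5, 10 and 12 points over the banded chi-square. The test must therefore be specified as 1 df to obtain the gain.

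Finally, the cuts are not arbitrary: the lowest band is a recognised status, and the literature review cites a study of monks with over 10 years. That supports keeping the bands for description. The background links MSD with longer ordination but does not place the rise after the first decade.

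**Conclusion.** The point holds in conditional form. For an objective about duration, the SAP defines only a three-band coding with an open top and does not say that the regression uses the recorded years. If the bands are used, no gradient or plateau beyond year 10 can be shown, and about 12% to 51% of the linear information is lost. Against a slope that recorded years would detect with 80% power, the banded chi-square has about 40% to 65%. To recover 80%, the bands would need roughly 560 to 1,010 participants instead of 400.

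These sizes rest on assumed spreads of years and a relation linear on the logit scale; the SAP gives neither. The direction is firmer: one linear term in recorded years had more power than either banded test under all six simulated spreads. If the whole relation is a step in the first decade, the bands lose little and can do somewhat better. The document does not support saying that the plan discards half the data or cannot detect a late rise.

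**What to change.** In the Statistical Analysis section, state that the main test of Hypothesis 1 is a logistic regression of MSD on years of monasticism as recorded on the form, entered as a single linear term (1 df). Add a quadratic or spline term as a separate check of shape, not as part of the main test. Describe the three bands and the chi-square as descriptive. Optionally, split the top band in the prevalence table, for example at 20 and 30 years; those cuts are only illustrative.

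The cost is one or two sentences and perhaps a few table rows, with no new data. The downside is somewhat less power than the bands if the whole relation is a step in the first decade.

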#### **Inclusion criteria:**

- 1- Both genders will include in study.
- 2- Monks and nuns work in different works administration.
- 3- Age starts from 24 years old and more. (Merakou, et al., 2017)
- 4- Body mass index (BMI) between 18.5 to 24.9 kg/m2 (Van, et al., 2023)

#### **Exclusion criteria:**

- 1- Monk or nun had musculoskeletal abnormalities due to causes (congenital or traumatic).
- 2- Monk or nun with previous operation involving locomotor system.
- 3- Outside body mass index range.

### instrumentations:

-All data collected by E-mailed Nordic questionnaire which availed, reliable and multiple part questionnaire. (Salik and Özcan., (2007)(appendix II)

## The questionnaire had four sections:

- **section** A– collected the Sociodemographic information:

- Age and gender, duration of ordination and type of professional work.
- **section B** Musculoskeletal disorders resulting from work:
- **section** C collection information of ergonomic features:
  - weight and height.
  - praying hours in standing position.
  - Working hours in the sitting position or standing position.
  - Others: any activities in daily life of monk.
- section D assess occurrence of musculoskeletal complaints the questionnaire divide back region to cervical, upper back and lower back.

section D as our study done on upper and lower back includes diagrams clearly marked.

## **Data Analysis:**

The data will be collected from questionnaires which are on answered by monks and nuns who live in different monasteries in Egypt.

## **Statistical Analysis:**

Descriptive statistics of mean and standard deviation, frequencies, percentage and confidence interval (CI) are utilized in presenting the subjects demographic and musculoskeletal disorders data. Person's chi – square statistic and logistic regression is utilized to examine associations between musculoskeletal disorders prevalence and years of ordination. The level of significance for all statistical tests is set at p<0.05. All statistical measure will be performed through the statistical package for social studies (SPSS version 22 for windows)

#### **Ethical Considerations:**

All participants will sign a consent form to declare that they are not forced to Participate in this study

